#### Comorbidities

- Asthma
- Non-malignant blood disorders, including sickle cell disease
- Chronic lung disease, including chronic obstructive pulmonary disease (COPD)
- Down syndrome
- Heart disease
- History of SARS-CoV-2 infection
- Immunocompromised status (i.e., history of human deficiency virus [HIV]; organ, bone marrow or stem cell transplant; use of immunosuppressant medication)
- Kidney disorders, including chronic kidney disease
- Liver disorders
- Neurological or neurodevelopmental conditions
- Malignant neoplasms
- Obesity
- Type 2 diabetes

#### **Prior COVID-19 Vaccination – Descriptive only (not for inclusion in PS model)**

- Receipt of COVID-19 vaccine doses (any brand) prior to 2023-2024
  - Because COVID-19 vaccination in the 270 days prior to cohort entry is an exclusion criterion ([Section 9.2.2.2](#)), this variable will only capture COVID-19 vaccinations in the 365 days through 271 days prior to cohort entry
- Days from the most recent prior COVID-19 vaccine dose (any brand) to first vaccination with 2023-2024 formulations (for all Phase 1 individuals, as well as Phase 2 individuals receiving COMIRNATY or another 2023-2024 formulation)

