## 7. RATIONALE AND BACKGROUND

The development of vaccines against SARS-CoV-2 has been critical to ending the Coronavirus disease 2019 (COVID-19) pandemic. In the United States (US), the first to become available were the messenger RNA (mRNA) vaccines BNT162B2 (COMIRNATY) (Pfizer Inc/BioNTech, 2023) and mRNA-1273 (Moderna US, Inc., 2023). Authorized for emergency use by the US Food and Drug Administration (FDA) on 11 December 2020 and 18 December 2020, respectively, these first-generation vaccines contained a piece of the original SARS-CoV-2 virus's mRNA, instructing cells in the body to make the virus's distinctive "spike" protein and triggering an immune response (FDA, 2020a, 2020b; Nabizadeh et al., 2023). Beginning in August 2022, in response to the new circulating Omicron variant of SARS-CoV-2, the vaccines were adapted to add an mRNA component from the Omicron lineages BA.4 and BA.5, in addition to mRNA from the original viral strain, and were thereafter referred to as bivalent vaccines (FDA, 2022b, 2022c, 2022d). In September 2023, the COMIRNATY 2023-2024 Formula was approved for individuals  $\geq 12$  years of age. The Pfizer-BioNTech COVID-19 Vaccine 2023-2024 Formula was authorized under emergency use in individuals 6 months through 11 years of age. This new formulation contains a monovalent (single) mRNA component corresponding to the Omicron variant XBB.1.5 (FDA, 2023b). The Omicron XBB sublineage accounted for nearly all COVID-19 cases in the US in spring 2023 and remained the most common variant as of 08 July 2023 (CDC, 2020).

Based on data from the original COMIRNATY formula, the US prescribing information for COMIRNATY highlights the following warnings and precautions:

- "Postmarketing data demonstrate increased risks of myocarditis and pericarditis"
- "Syncope (fainting) may occur in association with administration of injectable vaccines, including COMIRNATY." (Pfizer Inc/BioNTech, 2023)

Additionally, the following serious adverse events have been observed after immunization with the Pfizer-BioNTech, Moderna, and Janssen vaccines as reported in the Vaccine Adverse Event Reporting System (VAERS): glomerulonephritis, herpes zoster, immune-mediated myositis, and relapsing or progressing MS (VAERS, 2023). More information is needed on whether the safety profile of the COMIRNATY 2023-2024 Formula remains consistent with the safety profile of the original formula in the overall population and subpopulations of interest.

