### 9.1.2. Cohort Design

Phase 2 will consist of a propensity score-matched cohort study of individuals with and without a recorded dose of the COMIRNATY 2023-2024 Formula, conducted within the ORD. During the accrual period of 11 September 2023 through 31 March 2024, individuals who receive the COMIRNATY vaccine will be classified as exposed, and those with no recorded vaccination with the COMIRNATY 2023-2024 Formula but who have a healthcare encounter will be classified as comparators. Propensity score matching will be performed to address control of potential confounding, with matching to be conducted within age group and calendar periods. Age group will be defined as: 6 months–4 years; 5–11 years; 12–17 years; 18–64 years; and  $\geq 65$  years, while calendar periods will be defined by 14-day increments (e.g., 01 September 2023 to 14 September 2023, 15 September 2023 to 28 September 2023). Alternate calendar periods (e.g., one month) may be empirically explored. Thus, within any given calendar period, comparators within the same age group will be matched without replacement to a COMIRNATY recipient on PS, down to a maximum allowable level of precision in the PS ([Section 9.7.2.1](#)). This will ensure a sufficient pool of comparators for stratified and/or subpopulation analyses ([Sections 9.7.2.3 & 9.7.2.4](#)).

These matched cohorts will be followed for up to one year for occurrence of safety outcomes. For this Phase 2 matched cohort study, the safety outcomes of interest are listed in [Section 9.3.2](#).

090177e1a5be86fe\Approved\Approved On: 19-Mar-2026 15:57 (GMT)

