#### **9.2.2.2. Exclusion Criteria**

Patients meeting any of the following criteria will not be included in Phase 2 of the study:

1. Are of unknown sex.
2. Have a missing month and year of birth.
3. Have received a COVID-19 vaccine in the 270 days prior to cohort entry date (as defined in Section 9.2.3).
4. Have received both the COMIRNATY 2023-2024 Formula and a COVID-19 vaccine other than the COMIRNATY 2023-2024 Formula on the cohort entry date (defined in Section 9.2.3).

In both phases of the study, when creating the analytic population for each specific safety outcome of interest, individuals will be excluded if they experienced that safety outcome during the portion of the baseline period designated as the clean period ([Section 9.2.4](#)).

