#### **9.2.4. Baseline Period**

The baseline period will consist of all continuously enrolled available time up to one year (365 days) prior to the vaccination date (SCRI) or cohort entry date (cohort study). Recognizing that narrower or specific windows of assessment may better capture select patient attributes of interest, specific covariates may be assessed using alternate time period(s). In this study, all individuals are required to have a minimum of 365 days of continuous health plan enrollment prior to the vaccination or cohort entry date (Sections 9.2.1.1 and 9.2.2.1), or continuous enrollment since birth if the vaccination or cohort entry date occurred at  $< 1$  year of age.

In both study designs, some or all of the baseline period will be used to exclude individuals with prevalent outcomes prior to vaccination or cohort entry date. This portion of the baseline period will be referred to as the ‘clean period.’ For a list of outcome-specific clean periods, please see [Section 9.3.2](#).

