### **COVID-19 Vaccination – Descriptive only (not for inclusion in PS model)**

- Site of vaccination (e.g., outpatient, pharmacy)
- Source of vaccination information (e.g., CPT code, NDC)
- Number of doses prior to 2023-2024, by vaccine product
- Average number of days between doses of COMIRNATY 2023-2024 Formula, among those with multiple doses

Code lists for covariates are included in [Appendix IV](#).

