#### 9.7.2.4. Subgroup Analysis

If sample size permits, the main analysis will be restricted to the following subgroups:

- Individuals with concomitant administration of a non-COVID-19 vaccine (e.g., seasonal influenza, RSV) on cohort entry date; specific analyses will be performed among individuals receiving seasonal influenza vaccine and those receiving RSV vaccine
- Immunocompromised individuals
- Individuals with specific baseline comorbidities, such as a chronic lung, heart, kidney or liver condition; cancer; Down syndrome or other neurological or neurodevelopmental disorders; and blood disorders
- Individuals with prior SARS-CoV-2 infection
- Individuals with prior COVID-19 vaccination
- Pregnant women
- Individuals aged < 18 years
- Individuals aged  $\geq$  65 years

For the subgroup analysis, the propensity score will be included in the model as a covariate, given that some matched strata may be broken by restricting both the COMIRNATY 2023-2024 Formula cohort and the comparator cohort by the above attributes. As with the primary analysis, unconditional Poisson regression will be used, and the model will account for individuals who are included in both groups.

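### The prior COVID-19 vaccination subgroup captures only doses given 271 to 365 days before cohort entry, so it is mislabelled and only partly addresses its secondary objective

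*Protocol*

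**What the plan says.** Three provisions of the protocol combine.

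- Section 9.2.4 caps the look-back: "The baseline period will consist of all continuously enrolled available time up to one year (365 days) prior to the vaccination date", or the cohort entry date in Phase 2.
- Section 9.2.2.2 excludes from Phase 2 those who "Have received a COVID-19 vaccine in the 270 days prior to cohort entry date".
- Section 9.3.3, on prior COVID-19 vaccination, draws the consequence: "this variable will only capture COVID-19 vaccinations in the 365 days through 271 days prior to cohort entry". The variable is binary, descriptive, and kept out of the propensity score.

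The secondary objective (Section 8.2.2) lists people with prior COVID-19 vaccination among its subgroups, if sample size permits. Section 9.7.2.4 plans to restrict the main analysis to "Individuals with prior COVID-19 vaccination" and gives no other definition of prior.

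Section 9.9 calls vaccination in the previous year uninformative because of this window, but uses that only to explain its absence from the propensity score. Section 9.3.3 also lists a second descriptive item, "Number of doses prior to 2023-2024, by vaccine product". Section 9.2.4 allows other assessment periods for particular covariates, but the protocol does not use that allowance here.

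**The concern.** A reader of the final report will take a result for people with prior COVID-19 vaccination at face value. Doses have been available since December 2020, and someone vaccinated and boosted in 2021 to mid-2022 with no later dose belongs to that group in ordinary usage. Under Section 9.3.3 that person is coded as having no receipt and is left out of the subgroup, whatever the entry date.

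Membership also depends on when a person enters the study. Two people with the same vaccination history can fall on different sides of the line because one entered in October and the other in February.

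What is at stake is the meaning and generalisability of a subgroup result named in the secondary objective of a post-authorization safety study. The limitation is disclosed for a different purpose and is not carried to the subgroup it affects.

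**Working it through.** **Inputs**

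- Look-back of at most 365 days (Section 9.2.4); exclusion of 270 days (Section 9.2.2.2).
- Entry dates: "During the accrual period of 11 September 2023 through 31 March 2024" (Section 9.1.2).
- First emergency authorizations of the two mRNA vaccines: "on 11 December 2020 and 18 December 2020, respectively" (Section 7).
- Bivalent doses began in August 2022 (Section 7), and most bivalent recipients were dosed before March 2023 (Section 9.2).

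**Step 1: the stated window.** Days −365 to −1, less days −270 to −1, leaves days −365 to −271. This reproduces Section 9.3.3. Its length is 365 − 271 + 1 = 95 days, or 95/365 = 26% of the baseline year.

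**Step 2: calendar dates.** The window opens at entry − 365 and closes at entry − 271.

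| Cohort entry | Window opens | Window closes |
|---|---|---|
| 11 Sep 2023 | 11 Sep 2022 | 14 Dec 2022 |
| 31 Oct 2023 | 31 Oct 2022 | 2 Feb 2023 |
| 15 Dec 2023 | 15 Dec 2022 | 19 Mar 2023 |
| 29 Feb 2024 | 1 Mar 2023 | 3 Jun 2023 |
| 31 Mar 2024 | 1 Apr 2023 | 4 Jul 2023 |

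The earliest visible dose across all of accrual is 11 September 2022. A last dose between 11 December 2020 and 10 September 2022 is never flagged. From entry on 29 February 2024 the window opens after the period in which Section 9.2 places most bivalent uptake.

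**Step 3: share of previously vaccinated, eligible people who are flagged.** This depends on the dates of last doses, which the protocol does not give. Two assumptions show the range. In both, people dosed within 270 days are removed, because they are excluded from the study.

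*Assumption A:* last doses uniform from 11 December 2020 to day −271. Share = 95 / (days in that span).

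- Entry 11 Sep 2023: 95/734 = 12.9%.
- Entry 31 Mar 2024: 95/936 = 10.1%.

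*Assumption B:* every last dose bivalent, uniform over the 182 days from 31 August 2022 to 28 February 2023. Share = days captured / (days captured + days before the window).

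| Entry | Captured | Before window | Excluded | Share flagged |
|---|---|---|---|---|
| 11 Sep 2023 | 95 | 11 | 76 | 95/106 = 90% |
| 1 Oct 2023 | 95 | 31 | 56 | 95/126 = 75% |
| 31 Oct 2023 | 95 | 61 | 26 | 95/156 = 61% |
| 15 Dec 2023 | 76 | 106 | 0 | 76/182 = 42% |
| 31 Jan 2024 | 29 | 153 | 0 | 29/182 = 16% |
| 29 Feb 2024 | 0 | 182 | 0 | 0% |

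**Step 4: the dose count.** A count of doses by product before 2023-2024 calls for vaccination history. Under the one-year baseline and the 270-day exclusion it could count only doses that fall within the 95 days. The two items in Section 9.3.3 need to be brought into line.

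**The case against.** The other side has real points.

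- **Validity inside the subgroup.** Everyone flagged has a recorded dose. Unflagged people are not analysed as a contrast group, so incomplete capture shrinks the subgroup without contaminating it. This stands.
- **Bias between arms.** Comparators are matched within 14-day calendar periods, so both arms look back over nearly the same dates. Where restriction breaks matched sets, Section 9.7.2.4 adds the propensity score, whose model contains calendar month. This also stands: the sliding window limits whom the result describes, and no differential error between arms has been shown.
- **Disclosure.** Sections 9.3.3 and 9.9 state the narrow capture. This stands only in part, because neither Section 9.9 nor Section 9.7.2.4 says that the subgroup inherits it.
- **The late-entry example is a tail.** Section 9.2 expects uptake like the previous season's, when most bivalent recipients were dosed before March, so entrants from 29 February 2024 should be few. Fair, but under Assumption B the shift is already large by mid-December.

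A reader might go further and infer that most previously vaccinated people are classed as never vaccinated, so that the objective is not met. The protocol does not support this. It gives no distribution of last-dose dates, and Assumption B puts the flagged share at about 60% to 90% for entry from 11 September to 31 October 2023. It labels nobody as never vaccinated; the code is no receipt within the window. Nor is 95 of the 1,004 days from 11 December 2020 to 11 September 2023 (9%) a measure of people missed: it is a share of calendar days, and its denominator includes the 270 days whose recipients are excluded altogether.

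**Conclusion.** The point holds as one of definition and labelling. Followed as written, the plan will report a result for prior COVID-19 vaccination that applies to people dosed about 9 to 12 months before entry, in a window whose calendar position moves by more than six months over accrual. The objective, which is conditional on sample size, is partly addressed.

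The 95-day length, the window dates and the 11 September 2022 floor are exact and need no assumption. The share of previously vaccinated people left out is not known: the 10–13% and 90%-to-0% captured figures illustrate how far it depends on dose timing and are not estimates. The conclusion assumes that the Section 9.3.3 definition governs the Section 9.7.2.4 subgroup, which is the only reading the text offers. Section 7 describes the document as a combined protocol and SAP, so the definition has not visibly been left to another document.

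**What to change.** **Preferred: relabel.**

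- Rename the subgroup in Section 9.7.2.4, and the matching part of the secondary objective wherever it appears, as *COVID-19 vaccination 271 to 365 days before cohort entry*.
- Extend the Section 9.9 limitation to this subgroup, noting that its calendar window shifts with entry date and that no dose before 11 September 2022 is visible.
- In Section 9.3.3, either drop the dose count by product or state the period over which it is counted.

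This is a wording change that needs no new data. Its price is a narrower claim.

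**Alternative: lengthen the look-back for this variable only.** Use all available enrolment history before entry, which Section 9.2.4 permits and for which Section 9.4.2 describes a database reaching back well before 2020. State the costs:

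- Only 365 days of enrolment are required, so look-back length would vary between people.
- Section 9.6 ties each extract's timeframe to the baseline period and plans one extraction per report. The extract would have to reach further back, with the analytic dataset planned for 31 August 2025 and the final report for 30 April 2026 (Section 6).
- Section 9.9 says that vaccines given without insurance information may be missed, and that free doses outside insurance were easier to obtain in earlier years. Older doses would be under-captured, so an unflagged person still could not be read as unvaccinated.

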#### **Healthcare Utilization**

- Number of hospitalizations in prior year (continuous)
- Number of emergency room visits in prior year (continuous)
- Number of outpatient encounters in prior year (continuous)
- Other recorded vaccines administered
  - Seasonal influenza
  - RSV

#### **Medication History**

- Systemic immunomodulators
- Oral corticosteroids
- Antivirals
- Antibiotics

In addition to the covariates listed above, baseline attributes will be identified on an empiric basis by examining the 25 most frequently occurring diagnoses, drugs dispensed, and procedures (including other baseline vaccinations, as captured through NDC and CPT codes) performed among individuals with and without COMIRNATY 2023-2024 Formula exposure.

These empiric covariates will be considered for inclusion in the PS models if they are potential confounders.

### **COVID-19 Vaccination – Descriptive only (not for inclusion in PS model)**

- Site of vaccination (e.g., outpatient, pharmacy)
- Source of vaccination information (e.g., CPT code, NDC)
- Number of doses prior to 2023-2024, by vaccine product
- Average number of days between doses of COMIRNATY 2023-2024 Formula, among those with multiple doses

Code lists for covariates are included in [Appendix IV](#).

## **9.4. Data Sources**

The patients included in this study will be drawn from the Optum pre-adjudicated claims database for the interim reporting to expedite the identification of vaccinated patients, and from the ORD for the final reporting. These data sources are described below.

### **9.4.1. Optum Pre-Adjudicated Claims Database**

The database includes pre-adjudicated medical claims, supplemented with adjudicated pharmacy claims and health plan enrollment information. As claims for pharmacy services are typically submitted electronically by the pharmacy at the time prescriptions are filled or vaccinations are administered and are updated in the underlying database on a weekly basis, they are not included in the pre-adjudicated feed. The pre-adjudicated medical claims encompass hospital and physician claims that are submitted and processed daily from a large US commercial health plan. The individuals included in the pre-adjudicated medical claims database are fully insured by the health plan, which provides reimbursement of medical and pharmacy services regardless of site of care, and individuals are geographically diverse within the US. The claims adjudication process involves numerous assessments and adjustments and may result in claims being returned to the provider for revision or sent for payment processing. The pre-adjudicated claims are maintained in a database that allows for the capture of up to three years of prior data. These pre-adjudicated claims have been used for research previously, and for federally funded public health surveillance ([Dore et al., 2012](#); [FDA, 2021b](#); [Shoabi et al., 2023](#); [Wong et al., 2023](#); [Moll et al., 2023](#); [Schneider et al., 2023](#)).

The data include demographics, details from pharmacy claims (reflecting dispensings), and all pre-adjudicated medical and facility claims, including information on the types of services

---

 CPT copyright 2024 American Medical Association. All rights reserved.

*Fee schedules, relative value units, conversion factors and/or related components are not assigned by the AMA, are not part of CPT, and the AMA is not recommending their use. The AMA does not directly or indirectly practice medicine or dispense medical services. The AMA assumes no liability for data contained or not contained herein.*

*CPT is a registered trademark of the American Medical Association.*

or procedures and their accompanying diagnoses. The coding of medical claims conforms to insurance industry standards, including:

- Use of designated claims forms (e.g., physicians use the CMS-1500 format and hospitals use the UB-04 format)
- International Classification of Diseases, 10th Revision, Clinical Modification (ICD-10-CM) diagnosis codes and procedure codes
- Current Procedural Terminology (CPT-4®) codes
- Centers for Medicare and Medicaid Services (CMS) HCPCS codes

Claims for pharmacy services are typically submitted electronically by the pharmacy at the time prescriptions are filled. These data allow for longitudinal tracking of medication refill patterns and changes in medications and include:

- NDC
- Drug name
- Dosage form
- Drug strength
- Fill date
- Days of supply
- Cost information
- De-identified patient and prescriber codes

#### **9.4.2. Optum Research Database**

The ORD is a proprietary research database containing eligibility and adjudicated pharmacy and medical claims data from a large US health plan affiliated with Optum. The individuals covered by this health plan are geographically diverse across the US. As early as 1993, medical and pharmacy claims data are available for 70 million individuals with both medical and pharmacy benefit coverage. In 2021, data were available for approximately 12.6 million individuals with medical and pharmacy coverage. Optum research activities use de-identified data from the research database. In limited instances, patient identifiers may be accessed where applicable law allows the use of patient-identifiable data, and when the study obtains appropriate approvals for accessing data that are not de-identified.

#### **9.5. Study Size**

The sample size achieved will depend on the number of recipients of the COMIRNATY 2023-2024 Formula in the databases. All individuals who meet the study's eligibility criteria during the study period will be included.

#### **9.6. Data Management**

All analyses will be conducted using Statistical Analysis System (SAS) version 9.4 (SAS Institute Inc., Cary, North Carolina) and SAS Enterprise Guide 6.1 or later. The data will be

---

 CPT copyright 2024 American Medical Association. All rights reserved.

extracted once per report. All reports will utilize the structured data only. The interim report will include summarized results from the Optum pre-adjudicated claims database described in [Section 9.4.1](#). The final report will include results summarized from the ORD as described in [Section 9.4.2](#). The characteristics of patients to be included in each data extract (e.g., required vaccine codes) and the specific timeframes of each data extract will reflect the study inclusion/exclusion criteria described in [Section 9.2](#), the baseline and follow-up periods in [Sections 9.2.4](#) and [9.2.5](#), and the study variables in [Section 9.3](#). All reports and deliverables will contain aggregated results only and will not identify individual patients, physicians, or facilities.

